3. STUDY OBJECTIVES AND ENDPOINTS

3.1. Primary Objective

DOSE ESCALATION PHASE (STAGE 1)

The primary objective of the dose escalation phase (Stage 1) is to determine maximum tolerated dose (MTD) and/or recommended phase 2 dose (RP2D) of HMPL-689 in patients with relapsed, refractory, or resistant lymphoma.

DOSE EXPANSION PHASE (STAGE 2)

The primary objective of the dose expansion phase (Stage 2) is to further evaluate safety and tolerability of HMPL-689 at MTD in patients with relapsed, refractory, or resistant lymphoma.

3.2. SECONDARY OBJECTIVES

The secondary objectives are (for both stages):

- To assess preliminary efficacy of HMPL-689 in patients with relapsed, refractory, or resistant lymphoma overall and by lymphoma sub-types as assessed by investigator.
- To characterize PK parameters of HMPL-689 in patients with relapsed, refractory, or resistant lymphoma at both dose escalation and dose expansion stages.
- To evaluate the effect of HMPL-689 on cardiac repolarization, as detected by changes in electrocardiogram (ECG) QTc intervals.

Table 1 Objectives and Corresponding Endpoints

Tier Objectives and Corresponding Endpoints Endpoints		
Primary – Dose Escalation	•	 Incidence of DLTs Safety (including but not limited to TEAEs, treatment-related adverse events [TRAEs], SAEs, treatment-related SAEs [TRSAEs], and lab abnormalities)
Primary – Dose Expansion	To further evaluate safety and tolerability of HMPL-689 at MTD in patients with relapsed, refractory, or resistant lymphoma	Safety, including TEAEs and TRAEs
	To assess preliminary efficacy of HMPL689 in patients with relapsed, refractory, or resistant lymphoma overall and by lymphoma sub-types as assessed by investigator	 ORR TTR DoR CBR PFS
Secondary	To characterize PK parameters of HMPL-689 in patients with relapsed, refractory, or resistant lymphoma at both dose escalation and dose expansion stages	Concentration-time profiles and PK parameters after single dose and at steady state
	To evaluate the effect of HMPL- 689 on cardiac repolarization, as detected by changes in electrocardiogram (ECG) QTc intervals	QTc interval and HMPL-689 concentration

Abbreviations: CBR = clinical benefit rate; DLT = dose-limiting toxicity; DoR = duration of response; MTD = maximum tolerated dose; ORR = objective response rate; PD = progressive disease; PFS = progression-free survival; PK = pharmacokinetic; RP2D = recommended phase 2 dose; SAE = serious adverse event; TEAE = treatment-emergent adverse event; TRAE = treatment-related adverse event; TRSAE = treatment-related serious adverse event; TTR = time to response.

4. STUDY DESIGN

4.1. GENERAL DESCRIPTION

This is a Phase 1, open-label, multicenter study of HMPL-689 administered orally to patients with relapsed, refractory, or resistant lymphoma.

This study will consist of a dose escalation stage (Stage 1) and a dose expansion stage (Stage 2). Both Stage 1 and Stage 2 include the following periods: screening period, treatment period, safety follow-up period, and extended progression free survival (PFS) follow-up period, if applicable.

The study duration is estimated to be approximately 48 months.

Dose Escalation Stage (Stage 1)

Dose escalation will be performed according to a modified toxicity probability interval scheme-2 (mTPI-2). HMPL-689 will be titrated using a modified Fibonacci design allowing dose increments in subsequent dose levels. The dose escalation is planned at 5 mg once daily (QD), 10 mg QD, 15 mg QD, 20 mg QD, 25 mg QD, 30 mg QD, 35 mg QD, 40 mg QD, 45 mg QD, and 50 mg QD (dose levels 1–10). The need for dose escalation beyond 50 mg QD, or other regimens, such as twice daily, will be evaluated and determined by the safety review committee (SRC) based on all available cumulative clinical safety, PK, and efficacy data.

Dose Expansion Stage (Stage 2)

The safety, tolerability, PK, and preliminary efficacy of HMPL-689 at RP2D will be further evaluated in patients with relapsed/refractory/resistant non-Hodgkin lymphoma (NHL).

Patients will receive oral doses of HMPL-689 QD at the RP2D for continuous 28-day treatment cycles until disease progression, death, intolerable toxicity, at investigator's discretion that the patient can no longer benefit from the study treatment, patient withdrawal from the study, or the end of study, whichever occurs first.

CCI

4.2. DETERMINATION OF SAMPLE SIZE

In general, the maximum sample size in the dose-escalation stage will be determined by sponsor and investigator based on the accumulated safety data and the mTPI-2 design.

Patients who withdraw from the study prior to completing the DLT assessment window for reasons other than DLT or receive less than 75% of assigned study medication during DLT assessment window will be replaced. This may result in the actual enrollment exceeding the planned enrollment.

CCI

STAGE 1: DOSE ESCALATION STAGE

The maximum sample size at mTPI2 for this stage will be determined by sponsor and investigator based on the accumulated safety data and mTPI-2 design. The maximum sample size under the mTPI-2 method is $k \times (d+1)$, where k denotes the cohort size and d denotes the number of doses. The minimum cohort size in this study is 3 patients per cohort. To ensure that the highest dose (if needed) is reached per the mTPI-2 design and the availability of additional cohorts, it is estimated that approximately patients will be needed in this study.

Patients who withdraw from the study prior to completing the Dose-limiting toxicity (DLT) assessment window for reasons other than DLT or receive less than 75% of assigned study medication during DLT assessment window will be replaced. This may result in the actual enrollment exceeding the planned enrollment.

STAGE 2: DOSE EXPANSION STAGE

Sample size justification based on Protocol Amendment 4 is outlined in Protocol Section 7.1.

4.3. SCHEDULE OF EVENTS

Schedule of events can be found in Appendix 1 of protocol amendment 5.

5. PLANNED ANALYSES

There is no formal interim analysis planned for this study. However, the accrued data from any cohort may be analyzed for internal decision-making purposes.

A final analysis is planned for this study which will be performed at the end of study (defined as 18 months after the last patient has been enrolled in the study or all patients have discontinued the study treatment, whichever comes earlier in the protocol amendment 5) and after database lock.

6. ANALYSIS SETS

6.1. ALL ENROLLED SET

The all enrolled set will contain all patients who provide informed consent for this study.

6.2. FULL ANALYSIS SET (FAS)

The full analysis set (FAS) is defined as all patients who receive at least one dose of HMPL-689. The FAS will be used for analysis of safety data and efficacy endpoint PFS.

Patients will be analyzed by their actual dose initially received. If patients had their dose reduced during the study, all data will be summarized/analyzed based on the initial dose of study treatment received. However, some listings such as AE listings may give the actual dose to the patient received at the time of the AE (e.g. reduced dose, interruption etc.).

6.3. EFFICACY ANALYSIS SET (EAS)

The efficacy analysis set (EAS) is defined as all patients who receive at least one dose of HMPL-689 and have a baseline tumor assessment and at least one evaluable post-baseline assessment unless death occurs before the first post-baseline assessment. Anti-tumor efficacy endpoints: objective response rate (ORR), clinical benefit rate (CBR), time to

response (TTR), and duration of response (DoR) will be evaluated based on this analysis set.

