7.2 Analysis Populations

The following analysis populations are defined for the study:

Full Analysis Set (FAS):

The FAS is defined as all patients who receive at least one dose of HMPL-689. The FAS will be used for analysis of safety data and efficacy endpoint PFS.

DLT Evaluable Analysis Set: All patients enrolled in the dose escalation phase of the study who are evaluable for DLT assessment. A subject is DLT evaluable if he/she meets the following criteria:

- has received at least 75% of the assigned dose of study medication during the DLT assessment window

OR

- has not completed the DLT assessment period due to a DLT

Efficacy Analysis Set (EAS):

All patients who receive at least one dose of HMPL-689 and have a baseline tumor assessment and at least one post-baseline assessment will be considered evaluable for anti-tumor efficacy endpoints such as ORR, clinical benefit rate (CBR), TTR, and DoR.

Pharmacokinetics Analysis Set (PKAS):

The PKAS is defined as all patients who received at least one dose of HMPL-689 and have at least one PK sample obtained and analyzed.

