16. EFFICACY OUTCOMES

The EAS is the primary analysis set for disease response efficacy endpoints including ORR, CBR, DoR and TTR. The FAS is regarded as primary analysis set for PFS. In the evaluation of the tumor response endpoints (ORR, TTR, CBR, DoR, and PFS), the investigator-

assessed data will be utilized for tumor assessment. Unless otherwise specified, all efficacy outcomes are to be summarized by dose level in stage 1 and by the malignancy type in stage 2. Tumor assessment will be conducted every 8 weeks (±7 days) for the first 24 weeks and then every 12 weeks (±7 days) thereafter.

Tumor assessment in different types of malignancies will be evaluated according to specified guidelines/criteria:

- CLL: the modified International Workshop on CLL guideline (Hallek 2008, Cheson 2012), see Appendix 5 of protocol amendment 5.
- LPL/WM: consensus of international workshops on WM (IWWM-7 consensus)
 (Dimopoulos 2014), see Appendix 6 of protocol amendment 5.
- Other lymphomas: Lugano Response Criteria for Hodgkin and Non-Hodgkin Lymphoma (Cheson 2014), see Appendix 7 of protocol amendment 5.

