16.1. BEST OVERALL RESPONSE (BOR)

Best overall response is defined as the best response recorded from the start of treatment until disease progression or new anti-cancer therapy, whichever comes earlier.

Best overall response is determined from the sequence of responses assessed as below:

- For CLL guideline: Complete Response (CR), CR with incomplete bone marrow recovery (CRi), Partial Response (PR), Nodular Partial Response (nPR), Partial Response with Lymphocytosis (PR-L), Stable Disease (SD), Progressive Disease (PD), Not Evaluated (NE).
- For WM guideline: Complete Response (CR), Very Good Partial Response (VGPR), Partial Response (PR), Minor Response (MR), Stable Disease (SD), Progressive Disease (PD), Not Evaluated (NE).
- For Other Lymphomas guideline: Complete Response (CR), Partial Response (PR),
 Stable Disease (SD), Progressive Disease (PD), Not Evaluated (NE).

BOR will be assigned for each patient as the best response recorded from all responses recorded after study medication administration until disease progression or start of subsequent anti-tumor assessment, whichever comes earlier. For patients with multiple assessments on different dates for the same tumor assessment visit, the earliest date will be selected for PD, while the latest date will be selected for other responses.

Patients with BOR "NE" will be summarized by reason for having NE status. The following reasons will be used:

All post-baseline assessments have overall response NE

BOR data will be listed for all patients in EAS.

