16.3. COMPLETE RESPONSE RATE (CR RATE)

CR rate is defined as the proportion of patients who have BOR with CR or CRi for CLL patients, and CR only for other patients.

The estimated CR rate and 95% Clopper-Pearson confidence interval (CI) will be presented by dose level for Stage 1 and by the malignancy type for stage 2. CR rate data will be listed for all patients in EAS.

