16.5. PROGRESSIVE-FREE SURVIVAL (PFS)

PFS is defined as the time (in months) from the date of first study medication to the earliest date of disease progression or death of any cause, whichever occurs first.

Protocol Number: 2018-689-00US1 Page 32 of 43

Progression-free survival (PFS) (months) = (<date of progression or death or censoring > - <date of first dose of study medication> + 1)/30.4375.

A patient is deemed to be censored, according to the rules specified in Table 4 below:

Table 2 Progression-Free Survival Censoring Rule

-	Τ	D (CD :		E 4/6
#	Situation	Date of Progression	Outcome	Event/Censor reason
		or Censoring		
1	Death (without previously	Date of death	Event	Death
	documented progressive disease			
	[PD]) within two evaluable			
	tumor assessments[a] from last			
	evaluable tumor assessment or			
	first dose (if no post-baseline			
	tumor assessment)			
2	Death (without previously	Date of last evaluable	Censored	Death after two or more
	documented PD) after two or	tumor assessment or		consecutive missed or
	more consecutive missed/non-	date of first dose (if no		NE tumor assessments
	evaluable tumor assessments[a]	post-baseline tumor		
	from last evaluable tumor	assessment)		
	assessment or first dose (if no			
	post-baseline tumor assessment)			
3	Progression within two	Date of progression	Event	Disease Progression
	evaluable tumor assessments[a]			
	from last evaluable tumor			
	assessment or first dose (if no			
	post-baseline tumor assessment			
 	before PD)	D . Cl . 1 11		
4	Progression after two or more	Date of last evaluable	Censored	Progression after two or
	consecutive missed/non-	tumor assessment or		more consecutive
	evaluable tumor assessments ^[a]	date of first dose (if no		missed or NE tumor
	from last evaluable tumor	post-baseline tumor		assessments
	assessment or first dose (if no	assessment before PD)		
	post-baseline tumor assessment			
5	before PD)	Date of last evaluable	Censored	Deagrassian - A
3	Progression after new anti-		Censorea	Progression after new
	cancer treatment	tumor assessment before new anti-cancer		anti-cancer therapy
		treatment or date of		
		first dose (if no post-		
		baseline tumor		
		assessment before new		
		anti-cancer)		
6	No baseline tumor evaluable	Date of first dose	Censored	No baseline assessment
١	assessment and alive	Date of first dose	Censored	No baseine assessment
1	LASSESSIFICITE ALICE ALIVE		- 1	27 (1 1)
7		Date of first dose	Cencored	No noct-baceline

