7	No post-baseline tumor	Date of first dose	Censored	No post-baseline
	No post-baseline tumor evaluable assessment and alive			assessment
7 8	No post-baseline tumor evaluable assessment and alive New anti-cancer treatment	Date of last evaluable	Censored	assessment Initiation of new anti-
	No post-baseline tumor evaluable assessment and alive			assessment

		treatment or date of first dose (if no post- baseline tumor assessment before new anti-cancer)		
9	No disease progression or death Note: use last tumor assessment before two or more consecutive missed/non-evaluable tumor assessments (if exists)	Date of last evaluable	Censored	Progression free at time of analysis: the patient is known to be alive without any progression happened at the data cut- off date

Note: Only for tumor assessments and death date before cutoff date.

[a] time period that identifies two consecutive missed/non-evaluable tumor assessments is calculated as 2*(the planned duration between assessments + protocol allowed visit window) from the last evaluable tumor assessment or (2*the planned duration between assessments + 1*protocol allowed visit window) from date of first dose (if no post-baseline evaluable tumor assessment).

According to protocol, tumor assessment will be conducted every 8 weeks for the first 24 weeks and every 12 weeks thereafter (±7 days). Given the schedules visit assessment scheme, the definition of two missed consecutive tumor assessment visit may vary, please refer to following rule:

- If the last evaluable tumor assessment before PD/death is on or before Day 105 (week 15, which is 8 weeks before week 24, and allowing for 7 days for early visit, hence 7*16 weeks 7 days for a late visit =Day 105), then two consecutive assessments equates to 126 days since last evaluable tumor assessment, allowing for early and late visits (2*8 weeks + 7 days for an early assessment + 7 days for a late assessment), or 119 days since date of first dose, allowing for late visit (2*8 weeks + 7 days for a late assessment).
- If the two missed assessments occur over the period when the scheduled frequency of tumor assessments change from 8-weekly to 12-weekly, which means last evaluable tumor assessment is from week 16 to 23 (Day 106 to Day 161), then two consecutive assessments equates to 154 days (7*8 weeks + 7*12 weeks + 7 days for an early assessment + 7 days for a late assessment) since last evaluable tumor assessment.

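### ORR, CBR and, by inference, CR rate are planned only on the efficacy analysis set with no all-treated rate beside them, and SAP 6.3 departs from Protocol 7.2 on who is in that set without saying so

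*SAP*

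**What the plan says.** **Set for response endpoints.** SAP 16 states: "The EAS is the primary analysis set for disease response efficacy endpoints including ORR, CBR, DoR and TTR". The word primary suggests a second set, but SAP 16.1 to 16.4 name none. SAP 7.9 takes the denominator of every percentage from the population of interest, so ORR and CBR are divided by the EAS count. For CR rate no set is named; SAP 16.3 says only that "CR rate data will be listed for all patients in EAS".

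**Definition of the EAS.** SAP 6.3 admits treated patients who "have a baseline tumor assessment and at least one evaluable post-baseline assessment unless death occurs before the first post-baseline assessment". Protocol 7.2 says that treated patients who "have a baseline tumor assessment and at least one post-baseline assessment will be considered evaluable for anti-tumor efficacy endpoints". The Protocol has neither the evaluable qualifier nor the early-death exception.

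**Use of the FAS.** SAP 6.2 says: "The FAS will be used for analysis of safety data and efficacy endpoint PFS". In the PFS censoring table (SAP 16.5, Table 2), row 6 ("No baseline tumor evaluable" assessment, and alive) and row 7 ("No post-baseline tumor evaluable assessment and alive") are both censored at first dose.

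**NE reasons.** SAP 16.1 summarises patients whose best overall response is NE by reason and lists one: "All post-baseline assessments have overall response NE".

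**The concern.** Patients can leave before a usable scan. The first scheduled tumor assessment is at 8 weeks (Protocol 4.1.5). Since Amendment 5, a patient who stops drug for a reason other than progression also leaves the study (Protocol 5.7.13 and 5.8.2). Protocol 6.3.1.9 allows an investigator to call clinical progression without further disease assessments. A patient who stops early by any of these routes and is alive has no evaluable post-baseline assessment and falls outside the EAS. Such a patient was treated and did not respond, yet no planned response rate counts them.

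The second issue is that the SAP changed the membership of the set from the Protocol and does not say so. A reader who takes the denominator from Protocol 7.2 will expect different patients from those analysed. The single NE reason in SAP 16.1 fits the Protocol's set better than the SAP's own.

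At stake is how the preliminary efficacy figures read. No error rate, power or decision rule depends on them. DoR and TTR use responders only and are unaffected.

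**Working it through.** The documents give no figure to reproduce: the Stage 2 sample-size text and its tables are redacted, and the number of patients in the FAS but not the EAS is not stated. Every N, responder count, k, a and d below is an assumption. Intervals are 95% Clopper-Pearson.

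**Step 1. EAS rate against all-treated rate.** Let N be treated patients, R responders among them, k patients outside the EAS and r responders among those k.

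EAS rate = (R - r)/(N - k). All-treated rate = R/N.

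For patients with no evaluable post-baseline assessment, r = 0, because no response can be recorded. Then EAS rate = (R/N) × N/(N - k). The multiplier is:

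- N = 10, k = 1: 10/9 = 1.11
- N = 20, k = 1: 20/19 = 1.05; k = 2: 20/18 = 1.11
- N = 30, k = 1: 30/29 = 1.03; k = 3: 30/27 = 1.11
- any N, k = 0: 1.00

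With N = 20:

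| k | ORR, 10 responders | CBR, 15 at SD or better | CR rate, 2 CRs |
|---|---|---|---|
| 0 | 10/20 = 50.0% (27.2 to 72.8) | 15/20 = 75.0% | 2/20 = 10.0% |
| 1 | 10/19 = 52.6% (28.9 to 75.6) | 15/19 = 78.9% | 2/19 = 10.5% |
| 2 | 10/18 = 55.6% (30.8 to 78.5) | 15/18 = 83.3% | 2/18 = 11.1% |

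With N = 40 and 20 responders, k = 4 gives 20/36 = 55.6% (38.1 to 72.1) against 20/40 = 50.0% (33.8 to 66.2).

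**Step 2. Where r = 0 is not assured.** A patient lacking only a baseline assessment may have later assessments. The EAS rate exceeds the all-treated rate only if r/k < R/N. With N = 20, R = 10, k = 2 and r = 1, the EAS rate is 9/18 = 50.0%, the same as 10/20. This group should be small: Stage 2 requires measurable disease except in CLL and WM/LPL (Protocol 5.1.1, criterion 6), and lesions are documented at screening (Protocol 5.7.13).

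**Step 3. Protocol set against SAP set.** Take patients with a baseline assessment and read evaluable as not NE. SAP Table 2 supports that reading, since it uses non-evaluable and NE interchangeably for the same censoring situation. Let a be patients whose post-baseline assessments are all NE, d deaths before the first assessment, and w living patients with no post-baseline assessment.

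- Protocol 7.2: n = N - d - w
- SAP 6.3: n = N - a - w
- SAP minus Protocol = d - a

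With N = 20, R = 10, w = 0 (all-treated rate 50.0% throughout):

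| a | d | Protocol | SAP |
|---|---|---|---|
| 2 | 1 | 10/19 = 52.6% | 10/18 = 55.6% |
| 1 | 2 | 10/18 = 55.6% | 10/19 = 52.6% |
| 1 | 1 | 10/19 = 52.6% | 10/19 = 52.6%, different patients |

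The sign depends on the data. The early-death exception taken alone lowers the SAP rate.

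**Step 4. NE reason.** On the same reading, a patient whose assessments are all NE has already been removed by SAP 6.3. An early death that SAP 6.3 keeps has no assessment to be NE, so the listed reason does not apply. SAP 7.10 treats a missing response as NE at a visit and does not cover a patient with no visit.

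**Illustration from the documents.** Protocol 2.3 reports the sponsor's phase 1 study in China as 31/60 = 51.7% among assessed patients, with 79 treated at that dose; 31/79 = 39.2%. This is an upper illustration only, because some of the 19 may not yet have reached a first scan.

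**The case against.** A response-evaluable set is a legitimate choice for a phase 1 trial. Protocol 7.2 assigns response to it and Protocol 4.1.2 lets non-evaluable patients be replaced. The endpoints are secondary and descriptive. All of that stands.

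Much of the missing information is also available. SAP 9.1 tabulates FAS and EAS counts and lists set membership by patient, SAP 16.5 tabulates PFS censoring reasons, and Protocol 7.3.4 lists response data for all patients. This is real but partial mitigation. The SAP narrows the response listings to the EAS (16.2 to 16.4), and a rate rebuilt by hand is not a planned output with an interval.

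The SAP also governs the programming: Protocol 7.3 leaves analysis details to it, and SAP 2 says it is based on Amendment 5. So there is one working definition, and what remains is an unrecorded departure with an undefined term.

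Several stronger readings are tempting and are not supported:

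- *The reported rates will be inflated.* The documents do not show that k exceeds zero.
- *The EAS rate can never be below the all-treated rate.* Step 2 shows that this is not assured for patients lacking only a baseline assessment.
- *Dropped patients count as failures nowhere.* Living ones are censored at first dose in PFS. A patient who dies after a non-evaluable first scan is also outside the EAS, but that death can be a PFS event under Table 2, row 1.
- *The NE-reason mismatch distorts a rate.* It affects only a label; early deaths stay in the denominator and cannot enter the numerator.

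**Conclusion.** The point holds as a recommended change. ORR and CBR, and by inference CR rate, have no planned all-treated counterpart, and the SAP's EAS differs from the Protocol's without explanation. For dropped patients who are non-responders, which is certain where there is no evaluable post-baseline assessment, the rate rises by the factor N/(N-k). That is 1.03 to 1.11 for the assumed group sizes of 10 to 30 with one to three dropped, and nothing if none are dropped. In the 20-patient ORR example the shift is at most 5.6 points, small beside the interval width. The denominators under the two EAS definitions differ by d - a, in either direction; this rests on reading evaluable as not NE, which Table 2 supports but SAP 6.3 does not state. The CR-rate part rests on its listing sentence alone.

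**What to change.** Make these changes in the SAP before database lock:

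1. Report ORR, CBR and CR rate with Clopper-Pearson intervals on the FAS beside the EAS. Count NE, missing and unassessed patients as non-responders and, for CBR, as having no clinical benefit.
2. Define evaluable in SAP 6.3, state how all-NE patients and deaths before the first assessment are handled, and add a note recording the departure from Protocol 7.2. A protocol amendment is not needed.
3. As housekeeping that changes no rate, name the analysis set for CR rate and align the NE reasons in SAP 16.1 with the sets used, for example by adding no post-baseline assessment and death before first assessment.

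The cost is SAP wording and one extra denominator, with no new data. The downside is that the additional FAS figure may be slightly lower and counts patients who left early for reasons unrelated to efficacy as failures. For that reason both rates should be shown, rather than one replacing the other.
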